7. ACTIONS REQUIRED FOR REPEAT EPISODES OF POTENTIAL HY'S LAW
8. REFERENCES

1. INTRODUCTION

During the course of the study the Investigator will remain vigilant for increases in liver biochemistry. The Investigator is responsible for determining whether a patient meets potential Hy's Law (PHL) criteria at any point during the study.

The Investigator participates, together with GEICAM clinical project representatives, in review and assessment of cases meeting PHL criteria to agree whether Hy's Law (HL) criteria are met. HL criteria are met if there is no alternative explanation for the elevations in liver biochemistry other than Drug Induced Liver Injury (DILI) caused by the Investigational Product (IMP).

The Investigator is responsible for recording data pertaining to PHL/HL cases and for reporting Adverse Events (AE) and Serious Adverse Events (SAE) according to the outcome of the review and assessment in line with standard safety reporting processes.

2. DEFINITIONS

Potential Hy's Law (PHL)

Aspartate Aminotransferase (AST) or Alanine Aminotransferase (ALT) $\geq 3 \times$ ULN **and** Total Bilirubin (TBL) $\geq 2 \times$ ULN at any point during the study irrespective of an increase in Alkaline Phosphatase (AP). The elevations do not have to occur at the same time or within a specified time frame.

Hy's Law (HL)

AST or ALT $\geq 3 \times$ ULN **and** TBL $\geq 2 \times$ ULN, where no other reason, other than the IMP, can be found to explain the combination of increases, e.g., elevated AP indicating cholestasis, viral hepatitis, another drug. The elevations do not have to occur at the same time or within a specified time frame.

3. IDENTIFICATION OF POTENTIAL HY'S LAW CASES

In order to identify cases of PHL it is important to perform a comprehensive review of laboratory data for any patient who meets any of the following identification criteria in isolation or in combination:

- ALT $\geq 3 \times$ ULN
- AST $\geq 3 \times$ ULN
- TBL $\geq 2 \times$ ULN

The Investigator will without delay review each new laboratory report and if the identification criteria are met will:

- Determine whether the patient meets PHL criteria (see Section 2 of this Appendix for definition) by reviewing laboratory reports from all previous visits.
- Promptly enter the laboratory data into the laboratory CRF.

4. FOLLOW-UP

4.1 Potential Hy's Law Criteria not met

If the patient does not meet PHL criteria the Investigator will:

- Perform follow-up on subsequent laboratory results according to the guidance provided in the Clinical Study Protocol.

4.2 Potential Hy's Law Criteria met

If the patient does meet PHL criteria the Investigator will:

- Notify the GEICAM representative who will then inform the central Study Team.
- GEICAM project representatives contacts the Investigator, to provide guidance, discuss and agree an approach for the study patients' follow-up and the continuous review of data. Subsequent to this contact the Investigator will:
- Monitor the patient until liver biochemistry parameters and appropriate clinical symptoms and signs return to normal or baseline levels, or as long as medically indicated.
- Investigate the etiology of the event and perform diagnostic investigations as discussed with the Study Physician.
- Complete the three Liver CRF Modules as information becomes available.

- If at any time (in consultation with the GEICAM project representatives) the PHL case meets serious criteria, report it as an SAE using standard reporting procedures.

5. REVIEW AND ASSESSMENT OF POTENTIAL HY'S LAW CASES

The instructions in this Section should be followed for all cases where PHL criteria are met.

No later than 3 weeks after the biochemistry abnormality was initially detected, the Study Physician contacts the Investigator in order to review available data and agree on whether there is an alternative explanation for meeting PHL criteria other than DILI caused by the IMP. The AstraZeneca Medical Science Director and Global Safety Physician will also be involved in this review together with other subject matter experts as appropriate.

According to the outcome of the review and assessment, the Investigator will follow the instructions below.

If there is an agreed alternative explanation for the ALT or AST and TBL elevations, a determination of whether the alternative explanation is an AE will be made and subsequently whether the AE meets the criteria for a SAE:

- If the alternative explanation is **not** an AE, record the alternative explanation on the appropriate CRF.
- If the alternative explanation is an AE/SAE, record the AE /SAE in the CRF accordingly and follow the GEICAM standard processes.

If it is agreed that there is **no** explanation that would explain the ALT or AST and TBL elevations other than the IMP:

- Report an SAE (report term 'Hy's Law') according to GEICAM standard processes.
- The 'Medically Important' serious criterion should be used if no other serious criteria apply.
- As there is no alternative explanation for the HL case, a causality assessment of 'related' should be assigned.

If, there is an unavoidable delay, of over 3 weeks, in obtaining the information necessary to assess whether or not the case meets the criteria for HL, then it is assumed that there is no alternative explanation until such time as an informed decision can be made:

- Report an SAE (report term 'Potential Hy's Law') applying serious criteria and causality assessment as per above.
- Continue follow-up and review according to agreed plan. Once the necessary supplementary information is obtained, repeat the review and assessment to

determine whether HL criteria are met. Update the SAE report according to the outcome of the review.

6. ACTIONS REQUIRED WHEN POTENTIAL HY'S LAW CRITERIA ARE MET BEFORE AND AFTER STARTING STUDY TREATMENT (NOT APPLICABLE)

7. ACTIONS REQUIRED FOR REPEAT EPISODES OF POTENTIAL HY'S LAW

This section is applicable when a patient meets PHL criteria on study treatment and has already met PHL criteria at a previous on study treatment visit.

The requirement to conduct follow-up, review and assessment of a repeat occurrence(s) of PHL is based on the nature of the alternative cause identified for the previous occurrence.

The Investigator should determine the cause for the previous occurrence of PHL criteria being met and answer the following question:

- Was the alternative cause for the previous occurrence of PHL criteria being met chronic or progressing malignant disease?

If No: Follow the process described in Section 4.2 of this Appendix.

If Yes: Determine if there has been a significant change in the patient's condition* compared with when PHL criteria were previously met.

- If there is no significant change no action is required.
- If there is a significant change follow the process described in Section 4.2 of this Appendix.

* A 'significant' change in the patient's condition refers to a clinically relevant change in any of the individual liver biochemistry parameters (ALT, AST or total bilirubin) in isolation or in combination, or a clinically relevant change in associated symptoms. The determination of whether there has been a significant change will be at the discretion of the Investigator, this may be in consultation with the GEICAM clinical project representatives if there is any uncertainty.

## ABBREVIATIONS AND DEFINITIONS

AE	Adverse Event
AESI	Adverse Events of Special Interest
AML	Acute Myeloid Leukaemia
BC	Breast Cancer
BRCA1	Breast Cancer type 1
BRCA2	Breast Cancer type 2
CB	Clinical Benefit
CBR	Clinical Benefit Rate
CI	Confidence Interval
CpG	5'-C—phosphate—G—3'
CR	Complete Response
CTCAE	Common Terminology Criteria for Adverse Events
DNA	Deoxyribonucleic Acid
DoR	Duration of Response
ECG	Electrocardiography
eCRF	Electronic Case Report Form (sometimes referred to as Clinical Report Form). An electronic form for recording study participants' data during a clinical study, as required by the protocol.
GCP	Good Clinical Practice
GEICAM	Spanish Breast Cancer Group
ICF	Informed Consent Form
IDMC	Interim Data Monitoring Committee
IEC	Independent Ethics Committee
ITT	Intent To Treat
MDS	Myelodysplastic Syndrome
MDS/AML	Myelodysplastic Syndrome/Acute Myeloid Leukaemia
NCI	National Cancer Institute
NGS panel	Next Generation Sequencing panel
OAE	Other significant Adverse Events
OR	Objective Response
ORR	Objective Response Rate

---

OS	Overall Survival
PARP	Enzyme Poly ADP Ribose Polymerase
PD	Progressive Disease or Programmed Death depending on the context
PFS	Progression-Free Survival
PR	Partial Response
RECIST	Response Evaluation Criteria in Solid Tumours
RNA	Ribonucleic Acid
SAE	Serious Adverse Event
SAP	Statistical Analysis Plan
SD	Stable Disease
TLFs	Tables, Listings and Figures
TN	Triple-Negative
TNBC	Triple-Negative Breast Cancer

## 1. INTRODUCTION

The purpose of this Statistical Analysis Plan (SAP) is to give a detailed description of the statistical analyses to be performed to generate the final report for GEICAM/2015-06 study (COMETA-Breast).

Based on published data included in the protocol and data from the full clinical program to date, it is anticipated that olaparib, an orally active inhibitor of the enzyme poly ADP ribose polymerase (PARPi), will have a positive benefit risk profile for the treatment of the minority well-defined population of advanced triple-negative breast cancer (TNBC) patients with the promoter methylation of *BRCA* genes.

The statistical analyses of this study will be the responsibility of GEICAM. The interpretation of these results will be the responsibility of the Chief Investigator of the study.

This document may modify the plans outlined in the protocol; however, any major modifications of the primary endpoint definition and/or its analysis will also be reflected in a protocol amendment.

All analyses will be performed using the SAS Enterprise Guide 5.1 version.

## 2. STUDY OBJECTIVES

### 2.1 Main Objective

- To analyse the olaparib efficacy in the treatment of patients diagnosed of advanced TNBC with *BRCA1* and/or *BRCA2* promoter methylation assessed in somatic DNA.

### 2.2 Secondary Objectives

- To analyse other efficacy measures.
  - Clinical Benefit Rate (CBR).
  - Duration of Response (DoR).
  - Progression Free Survival (PFS).
  - Overall Survival (OS).
- To analyse olaparib safety.

- To explore changes in the methylation status of *BRCA1/2* promoter in germline DNA prior and after treatment discontinuation for any reason and correlate germline *BRCA1/2* methylation data with efficacy parameters.
- To correlate *BRCA1/2* methylation between germline and somatic DNA and between primary tumour and metastatic lesions.
- To correlate *BRCA1/2* expression with methylation status of *BRCA1/2* promoter and efficacy parameters.

[figure not shown]
### 2.3 Exploratory Objectives

- Explore biomarkers of clinical activity in tumour and blood samples.

## 3. STUDY DESIGN

This is a multicenter, non-randomised, phase II clinical trial to assess the efficacy and safety of olaparib in monotherapy in patients diagnosed of advanced TNBC with methylation of *BRCA1* and/or 2 promoters (assessed in DNA from metastatic lesions) and absence of *BRCA1* and 2 germline mutations. Patients must have received at least one previous regimen in the advance disease setting.

### Figure 1 Study Design

Potential eligible patients will be screened to assess germinal (g) *BRCA* mutational status at Myriad laboratory (unless the *BRCA* mutational status is already known based on a Myriad previous report).

Blood samples for mutational *BRCA* screening could be sent either 1) during the previous line of treatment, once the eligibility criteria have been reviewed and the patient is considered a potential candidate for the study (at least the patient must have measurable and biopsiable disease) or 2)

after end of the line of treatment prior to study enrolment (simultaneously to the shipment of the tumour samples for methylation analysis). A specific Informed Consent Form (ICF) must be signed for this screening assessment.

Somatic (s) *BRCA* promoter methylation will be assessed also centrally at an external reference central laboratory selected by GEICAM. Tumour samples must proceed from a metastatic lesion, it is strongly recommended to obtain it after the line treatment immediately previous to the study entry.

Patients with a positive methylation status on *BRCA1* and/or *BRCA2* and lacking of known deleterious or suspected deleterious mutations in both genes could be included in the study to receive olaparib tablet formulation at 600 mg daily dose (given in two oral administrations of 300 mg every 12 hours approximately). Blood and tumour samples collected from all registered patients could be used for the secondary and exploratory analyses of the study, including but not limited to the assessment of germline methylation status and gene expression levels of *BRCA1/2*.

Patients will continue to receive their treatment until objective disease progression, symptomatic deterioration, unacceptable toxicity, death or withdrawal of consent, whichever occurs first.

Each assessment of tumour response will be performed as scheduled according to the calendar regardless of any dosing delay to prevent the introduction of bias into the assessment of efficacy.

According to RECIST v.1.1 in case of patients with a global deterioration of health status requiring discontinuation of treatment without objective evidence of disease progression at that time every effort should be made to document objective progression, even after discontinuation of treatment.

The objective response status of such patients should be determined considering RECIST v.1.1 instructions. In case any efficacy assessment cannot be done, they will be considered not evaluable for response rate analysis and PFS will be censored at the date of the last tumour assessment.

### 3.1 Sample Size

We have set the null hypothesis (H0) that ORR will be 30% (ORR achieved by TN patients treated with gemcitabine plus carboplatini) versus the alternative hypothesis (H1) that ORR will be 54% (ORR showed by TN *BRCA* mutated patients treated with olaparibii). Using an optimal two-stage Simon model and considering an alpha error of 0.05 and a statistical power of 80%, it will be required to include 31 evaluable patients. Twelve evaluable patients will be enrolled in the first

stage, and if at least 4 patients of them have response, additional patients will be recruited to get a total of 31 evaluable patients. Assuming a 10% dropout rate, the total number of patients to be enrolled is 34. Considering, these data the number of responders needed at the end of stage 2 to reject the null hypothesis is at least 14 responders.

### **3.2 Randomization**

Not applicable.

## **4. STUDY POPULATION**

### **4.1 ITT Population**

The Intent to treat population (ITT) will include all patients who are enrolled in the study.

### **4.2 Efficacy population**

A subset of the ITT population that have received at least one dose of study medication and has performed at least one tumour response assessment according to RECIST version 1.1 (unless PD, death or unacceptable toxicity is observed before the first tumour response assessment) and without major protocol deviations according to the protocol deviation manual.

### **4.3 Safety population**

Safety population will include all patients who are enrolled and have received at least one dose of the study treatment. This population is for the safety analysis.

### **4.4 Biomarker population**

A subset of enrolled patients with evaluable blood and/or tumour samples required for achievement of the secondary and exploratory objectives of the study.

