APTT	Activated Partial Thromboplastin Time
AR	Adverse Reaction
AST/ASAT (SGOT)	Aspartate Aminotransferase
BC	Breast Cancer
b.i.d.	Twice daily (from Latin Bis In Die)
BUN	Blood Urea Nitrogen
CBR	Clinical Benefit Rate
CI	Confidence Interval
Compliance	Adherence to all the trial-related requirements, good clinical practice (GCP) requirements, and the applicable regulatory requirements.
CR	Complete Response
CTCAE	Common Terminology Criteria for Adverse Events
CT Scan	Computed Tomography Scan
DLT	Dose-Limiting Toxicity
DNA	Deoxyribonucleic Acid
DoR	Duration of Response
DSB	Double Strand Break
DSUR	Development Safety Update Report
eCRF	Electronic Case Report Form (sometimes referred to as Clinical Report Form). An electronic form for recording study participants' data during a clinical study, as required by the protocol.
ECG	Electrocardiogram
ECOG	Eastern Cooperative Oncology Group
EE	Ethynodiol Diacetate
End of Study (Trial)	This study will be considered complete following the data cut-off date and datalock for the final analysis, the data cut-off date will be the date of last patient's death or the date when there is sufficient data to achieve the final analysis for primary and secondary objectives, whichever comes first
Enroll	The act of including a patient in the study. Patients who are enrolled in the trial are those who have been assigned a registration (or screening) number and it will be confirmed that the patient will receive the study treatment.
Screen	The act of obtaining informed consent for participation in a clinical trial from patients deemed eligible or potentially eligible to participate in the clinical trial. Patients entered into a trial are those who sign the informed consent document directly or through their legally acceptable representatives. Patients who are entered in the trial will be assigned a registration (or screening) number.

EOT	End of Treatment
ER	Oestrogen Receptor
ERB/IRB/IEC	Ethical review board/Institutional review board/Independent Ethics Committee: A board or committee (institutional, regional, or national) composed of medical professional and nonmedical members whose responsibility is to verify that the safety, welfare, and human rights of the patients participating in a clinical trial are protected.
ESR	Expedited Safety Report
et al	And collaborators
FDA	Food and Drug Administration
FFPE	Formalin-Fixed Paraffin-Embedded
gBRCA	BRCA1 and 2 in germinal line
GCP	Good Clinical Practice

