3.1. Study Design

This is a multicenter, non-randomized, phase II clinical trial to assess the efficacy and safety of olaparib in monotherapy in patients diagnosed of advanced triple negative BC with methylation of *BRCA1* and/or 2 promoters (assessed in DNA from metastatic lesions) and absence of *BRCA1* and 2 germline mutations. Patients must have received at least one previous regimen in the advance disease setting.

Figure 1 Study Design

Potential eligible patients will be screened to assess germinal (g) *BRCA* mutational status at Myriad laboratory (unless the *BRCA* mutational status is already known based on a Myriad previous report).

Blood samples for mutational *BRCA* screening could be sent either 1) during the previous line of treatment, once the eligibility criteria have been reviewed and the patient is considered a potential candidate for the study (at least the patient must have measurable and biopsiable disease) or 2) after end of the line of treatment prior to study enrolment (simultaneously to the shipment of the tumour samples for methylation analysis). A specific ICF must be signed for this screening assessment.

Somatic (s) *BRCA* promoter methylation will be assessed also centrally at an external reference central laboratory selected by GEICAM. Tumour samples must proceed from a metastatic lesion, it is strongly recommended to obtain it after the line treatment immediately previous to the study entry.

Patients with a positive methylation status on *BRCA1* and/or *BRCA2* and lacking of known deleterious or suspected deleterious mutations in both genes could be included in the study to receive olaparib tablet formulation at 600 mg daily dose (given in two oral administrations of 300 mg every 12 hours approximately). Blood and tumour samples collected from all registered patients could be used for the secondary and exploratory analysis of the study, including but not limited to the assessment of germline methylation status and gene expression levels of *BRCA1/2*.

Patients will continue to receive their treatment until objective disease progression, symptomatic deterioration, unacceptable toxicity, death or withdrawal of consent, whichever occurs first.

Each assessment of tumour response will be performed as scheduled according to the calendar regardless of any dosing delay to prevent the introduction of bias into the assessment of efficacy.

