4.1. Inclusion Criteria

Patients are eligible to be included in the study only if they **meet all** of the following criteria. Any asterisked* are also applicable as an inclusion criteria prior to perform the BRCA methylation testing via central testing; to perform the *BRCA* methylation test, investigator judgement of patient's potential eligibility to the study should be assessed as per Protocol Attachment 1. Study Schedule and by reviewing the below inclusion criteria):

1. *The patient has signed and dated the informed consent document and it has been obtained before conducting any procedure specifically for the study.
2. Female ≥ 18 years of age on day of signing informed consent.
3. Patient with histological confirmation of breast cancer with evidence of advanced disease not amenable to resection or radiation therapy with curative intent.
4. Documented **triple negative** disease by immunohistochemistry (IHC) and/or *in situ* hybridization based on local testing (preferably assessed on the most recent tumour biopsy available). TN is defined as **negative hormone receptor status** ($< 1\%$ of tumour cells with ER and PgR expression) and **HER2-negative status** (defined as IHC score 0/1+ or negative by *in situ* hybridization according to local criteria).
5. Patient must have received at least one previous regimen in the advance disease setting.
6. Absence of deleterious or suspected deleterious germline mutations in *BRCA1* and *BRCA2*. Germinal *BRCA* mutational status will be centrally assessed in Myriad laboratories to check eligibility unless the test has been previously performed at Myriad and absence of mutations has been determined.
7. Availability of a tumour tissue sample from the metastatic lesions (every effort should be done to obtain the sample after the previous therapeutic regimen for advanced disease) for central testing.
8. Documented methylation of *BRCA1* and/or 2 promoters based on central testing by analysis on the most recent tumour from metastatic lesions available.
9. At least one lesion measurable not previously irradiated, that can be accurately measured at baseline as ≥ 10 mm in the longest diameter (except lymph nodes which must have short axis ≥ 15 mm) with computed tomography (CT) or magnetic resonance imaging (MRI) or clinical examination and which is suitable for accurate repeated measurements according to RECIST v.1.1.

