	
- At the end of treatment (prior to next therapy regimen).
 
If a patient ends treatment due to other cause different to disease progression, one additional sample should be collected once progression is documented, if feasible.
	Required for all enrolled patients

Archival primary tumour sample (if available)	
 - To be collected during the study 	Required for all registered patients, if available
Biopsy from metastatic tumour sample at disease progression (if available)	
 - At disease progression If the patient ends the study due to disease progression, it must be collected prior to next therapy regimen. If the patient ends treatment due to other cause different to disease progression, collect this sample once progression is documented. 	Required for all enrolled patients, if available

The samples and data from this research will be coded and not identified with any personal details. Each sample will be identified with the study and patient number. In this way biomarker data may be correlated with clinical data, samples destroyed or returned in the event of withdrawal of consent and regulatory audit enabled. Access to the link between the biomarker sample and the individual patient are restricted to the Investigator and his collaborators, IEC, health authorities, monitors and auditors of the sponsor or its authorized agents, who are bound to secrecy inherent to their profession, when they are required to check the data and study procedures to ensure that the study is being done correctly and the data is accurate, but always maintaining the confidentiality of the same in accordance with current legislation.

6.3.2. *BRCA1 and BRCA2 Promoter Methylation Testing in Somatic DNA*

At least one paraffin sample from metastatic lesions is mandatory to perform methylation test and determine patient eligibility. Every effort should be done to obtain the sample after last treatment for metastatic disease, prior to the study entry. Surgery blocks or core biopsies would be acceptable, minimal amount of tumour tissue will be specified in the SMM.

Tumour samples for methylation screening analysis must be sent to the epigenetic central laboratory following shipment instructions in the SMM. Results from both analyses will be provided to Investigator within 8 working days after the day the samples are received in the central laboratory, unless extra-time is needed for justified reasons.

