The sBRCA methylation status result from the central laboratory assessment will be provided to the Investigator in order to determine subject eligibility. Investigator must explain to the patient that this assessment has unknown clinical significance in this moment and that the results of this trial will test the olaparib efficacy in patients with methylated sBRCA promoter, helping to elucidate if a relation between the methylation status and the response to olaparib may exist. If so, subsequent studies should be needed to confirm it.

DNA from paraffin-embedded tumour samples will be obtained in a central pathology laboratory and sent to the central epigenetics laboratory for methylation assessment. There, DNA will be treated with sodium bisulphite which will induce the deamination of cytosine

to uracil while 5-methylcytosine will remain as cytosine. *BRCA1* and 2 CpG island methylation status will be established using pyrosequencing, a semi-quantitative method that will give a methylation value of each of the CpG dinucleotides included in the sequence to be analyse. Samples will be processed per triplicate, computing for each promoter CpG island (*BRCA1* & *BRCA2*), average methylation values of CpG sites, considering as unmethylated whenever the value is lower than 25% ($\beta \leq 0.25$), while methylated status will be consider when methylation value is higher than 25% ($\beta > 0.25$). If a modification of the cut-off value is deemed necessary it will be established in laboratory manual.

Analysis will be performed using validated methods with defined acceptance criteria including the circumstances that require repeating analysis; positive and negative controls will be included in each analysis.

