8.2.1. Patient Populations

Intent to treat population (ITT): The ITT population will include all patients who are enrolled in the study.

Efficacy population: a subset of the ITT population that have received at least one dose of study medication and has performed at least one tumour response assessment according to RECIST v.1.1 (unless a progression, death or unacceptable toxicity is seen before the first tumour response assessment) and without major protocol deviations according to the protocol deviation manual.

The **efficacy** population will be the primary population for the efficacy analysis.

It will be performed a sensitivity analysis using the ITT population.

Safety population: will include all patients enrolled in the study who received at least one dose of treatment. This population is for the safety analysis.

Population for Biomarker Analysis: a subset of enrolled patients with evaluable blood and/or tumour samples required for achievement of the secondary and exploratory objectives of the study.

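### The Biomarker population is limited to enrolled patients, all selected for a methylated metastasis, which distorts the methylation concordance analyses and conflicts with the design text on using samples from all registered patients

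*SAP*

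**What the plan says.** **Population.** SAP 4.4 defines the Biomarker population as "A subset of enrolled patients with evaluable blood and/or tumour samples required for achievement of the secondary and exploratory objectives of the study". Protocol 8.2.1 uses the same restriction: "a subset of enrolled patients with evaluable blood and/or tumour samples", for the secondary and exploratory objectives. No other biomarker set is defined. The Protocol's definitions list separates enrolment from registration: for an enrolled patient, "it will be confirmed that the patient will receive the study treatment".

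**Selection.** Inclusion criterion 8 (Protocol 4.1) requires documented methylation of the BRCA1 and/or BRCA2 "promoters based on central testing by analysis on the most recent tumour from metastatic lesions available". Protocol 6.3.2 sets the threshold separately for each promoter: "while methylated status will be consider when methylation value is higher than 25" per cent.

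**Samples.** Protocol 3.1 states: "Blood and tumour samples collected from all registered patients could be used for the secondary and exploratory analysis of the study". Protocol 5.3 and SAP section 3 say much the same. In Table 13 (Protocol 6.3.1):
- screening blood for methylation and expression is required from every registered patient, with explicit timing for screening failures;
- archival primary tumour is "Required for all registered patients, if available";
- the metastatic screening sample is listed as an eligibility requirement, with leftover tissue kept for secondary and exploratory work.

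**Planned tests** (Protocol 8.2.8, SAP 9.2.3). Germline against somatic, and primary against metastatic, are compared through the paired difference of continuous values by t or Wilcoxon test. Expression against methylation uses chi-square when both are binary, and t or Wilcoxon when both are continuous. None of these paragraphs names an analysis set.

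**The concern.** Three secondary objectives ask how methylation measurements relate to each other or to expression: germline with somatic DNA, primary tumour with metastasis, and expression with promoter methylation. None of them involves response to olaparib, so nothing in them calls for treated patients only. Yet the only defined analysis set consists of patients chosen for a high value on one of the variables being compared.

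Two things are at stake. One is lost information: the patients with unmethylated metastases, who supply the contrast, are left out. The other is bias. A paired comparison in which only one side was selected to be high will show that side higher through regression to the mean. The trial could then report a gain of methylation in metastases that its own eligibility rule produced.

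The documents also pull in two directions. The design text permits use of all registered patients' samples; the population definition, which a programmer would follow, drops them.

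**Working it through.** **1. Numbers of patients.** The documents give no sample size for the biomarker objectives. The ceiling of the enrolled-only set is the planned enrolment of 34 (31 evaluable plus 10% dropout; 31/0.9 = 34.4). The synopsis plans 16 sites screening 7 or 8 each.
- Screened: 16 × 7 = 112 to 16 × 8 = 128.
- Registered but not enrolled: 112 − 34 = 78 to 128 − 34 = 94.

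This is an upper bound on added pairs. SAP 5.1 lists germline mutation, no tumour available and a non-assessable test as separate reasons for non-enrolment, and only patients who reached methylation testing have a metastatic value.

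**2. Binary expression against composite metastatic status.** Enrolled only, the table has at most 34 methylated and 0 unmethylated patients. The odds ratio is undefined and Fisher's exact p is 1 whatever the expression data.

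For contrast, take the 66% silencing among methylated tumours quoted in Protocol 1.2.2 and assume silencing of 10%, 20%, 30% or 40% in unmethylated tumours. Two-sided 5% power, pooled variance under the null:

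| Comparison | 10% | 20% | 30% | 40% |
|---|---|---|---|---|
| 34 vs 78 (all non-enrolled unmethylated and usable; best case) | >99% | 99.8% | 95% | 72% |
| 17 vs 39 (half the samples) | 99% | 93% | 72% | 43% |

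Check of 34 vs 78 at 40%: pooled proportion (22.44 + 31.2)/112 = 0.479; standard error under the null 0.1027, under the alternative 0.0984; z = (0.26 − 1.96 × 0.1027)/0.0984 = 0.60; power 72%.

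**3. Continuous values (illustration).** Assume metastatic value X and primary value Y are standard bivariate normal with equal means and true correlation ρ, and that patients enter when X lies in the top fraction f. The enrolled share of those screened is 34/128 = 0.27 to 34/112 = 0.30. Protocol 1.2.2 cites up to 40% of triple-negative tumours with methylated BRCA1. So f = 0.30 and 0.40 are shown.

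With c the cut-off, λ = φ(c)/f and v = 1 + cλ − λ²:
- restricted correlation = ρ√v / √(1 − ρ² + ρ²v);
- mean of X − Y among the selected = (1 − ρ)λ;
- SD of X − Y among the selected = √((1 − ρ)²v + 1 − ρ²).

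For f = 0.30: c = 0.524, λ = 1.159, v = 0.265. For f = 0.40: c = 0.253, λ = 0.966, v = 0.312. Rejection rates are simulated for a two-sided 5% paired t-test on 20 pairs.

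| f | True ρ | Restricted ρ | Spurious difference (SD units) | Rejection rate |
|---|---|---|---|---|
| 0.30 | 0.7 | 0.45 | 0.3 × 1.159 = +0.35 | 52–53% |
| 0.30 | 0.5 | 0.28 | 0.5 × 1.159 = +0.58 | 77–78% |
| 0.40 | 0.7 | 0.48 | 0.3 × 0.966 = +0.29 | 39% |
| 0.40 | 0.5 | 0.31 | 0.5 × 0.966 = +0.48 | 61–62% |

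The nominal rate is 5%. The ranges reflect separate simulation runs.

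**4. Information about association.** The power to detect a correlation is about Φ(atanh(r)√(n − 3) − 1.96). For a true ρ of 0.5, with f from 0.27 to 0.40, the restricted value is 0.28 to 0.31 and power at n = 34 is 35–42%. Unrestricted at n = 112, the upper bound, it exceeds 99%. The SAP specifies difference tests here, not a correlation coefficient, so this measures lost information rather than the power of a planned test.

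**The case against.** The strongest reply is that the documents already foresee wider use. Protocol 3.1 and SAP section 3 name germline methylation and expression among the uses of registered patients' samples, and the analysis paragraphs in SAP 9.2.3 name no population. On that reading only a clarification is missing. This stands in part: the defect is an unresolved conflict, and it is not certain that the analysis would be confined to 34 patients. But the design text is permissive, the definition in SAP 4.4 and Protocol 8.2.1 is explicit, and following the definition gives a biased comparison.

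Second, a reader might infer that somatic status cannot vary at all in the enrolled set. The documents do not support that. Eligibility is by either gene and methylation is called per promoter, so a patient methylated for BRCA1 may be unmethylated for BRCA2. Continuous values vary above the threshold. Germline, primary-tumour and progression-biopsy values are not fixed by selection. Nor does the SAP specify a two-by-two table of germline against somatic status, so the empty-row argument applies only to expression against composite metastatic status.

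Third, the magnitudes rest on assumptions from outside the documents: normality, equal means, the true correlations, the selected fraction and 20 pairs. Selection on either of two genes truncates each gene less sharply than the one-variable model. Equal means should not be carried over to blood against tumour, since Protocol 1.2.2 reports higher methylation in tumour than in matched blood. These limits are fair; the direction of the bias does not depend on the exact figures.

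Fourth, the affected objectives are secondary, and the SAP already makes biomarker tables subject to feasibility. That bears on priority, not on whether the set is right.

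**Conclusion.** The concern holds in this form. Applied as written, the population rule makes the chi-square of expression against composite metastatic status uninformative. It also truncates one side of the primary-metastatic and germline-somatic comparisons, weakening association and biasing the metastasis-minus-primary difference upward. It contradicts the design text in both documents. Under the stated illustration the spurious difference is about 0.3 to 0.6 SD, and the paired test rejects far more often than 5%. These are not estimates of the trial's actual error rate.

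Two stronger readings should be avoided. One is that Table 13 requires metastatic tissue from every registered patient: it ties that sample to eligibility, and the germline blood test may be sent earlier, so a mutation carrier may never supply one. The other is that 78–94 unmethylated pairs are being discarded: that figure is a ceiling that includes other kinds of screening failure.

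Response rate and safety are untouched. Germline pre/post change and correlations with efficacy properly use enrolled patients. This should be corrected, but it does not threaten the trial's main conclusion.

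**What to change.** In SAP 4.4 and Protocol 8.2.1, replace the single Biomarker population with two sets, and name the set under each objective in SAP 9.2.3:

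- **Concordance set:** all registered patients with the relevant evaluable paired samples, for the germline-somatic, primary-metastatic and expression-methylation analyses. Report BRCA1 and BRCA2 separately, with the enrolled-only result as a secondary display.
- **Outcome set:** enrolled patients with evaluable samples, for pre/post change and any analysis against efficacy.

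Report how many registered patients contribute to each pairing and why the others do not.

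The cost is wording in both documents plus assay runs on screening-failure samples that the protocol already collects. No new patients or procedures are needed. The gain is limited by residual metastatic tissue and by the availability of archival primaries, neither of which the documents quantify.
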